## 6.2 Exclusion criteria

- Bilateral breast cancer
- Evidence of distant metastases (M1)
- Patients who have received previous treatment for invasive breast cancer
- Concomitant active malignancy except for adequately treated carcinoma in situ of the uterine cervix or basal cell carcinoma of the skin
- Co-morbid disease which would preclude safe surgical treatment of the primary cancer
- Other physical or psychiatric disorder that may interfere with subject compliance, adequate informed consent or determine the causality of adverse events
- Contraindications to celecoxib: active peptic ulcer disease, renal impairment, asthma exacerbated by NSAIDs, congestive cardiac failure (NYHA II-IV\*), ischaemic heart disease, cerebrovascular disease, uncontrolled hypertension

### \*NYHA classification

Class I: Patients with cardiac disease but without resulting limitations of physical activity. Ordinary physical activity does not cause undue fatigue, palpitation, dyspnoea or anginal pain.

Class II: Patients with cardiac disease resulting in slight limitation of physical activity. They are comfortable at rest. Ordinary physical activity results in fatigue, palpitation, dyspnoea or anginal pain.

Class III: Patients with cardiac disease resulting in marked limitation of physical activity. They are comfortable at rest. Less than ordinary physical activity causes fatigue, palpitation, dyspnoea or anginal pain.

Class IV: Patients with cardiac disease resulting in inability to carry on any physical activity without discomfort. Symptoms of cardiac insufficiency or of the anginal syndrome may be present even at rest. If any physical activity is undertaken, discomfort is increased.

- Patients with an ongoing requirement for regular NSAID or COX 2 inhibitor therapy (Asprin 75mg daily is permitted)
- Regular selective COX 2 inhibitor use in the 2 years prior to randomisation
- History of hypersensitivity to celecoxib, exemestane or letrozole or to any of the excipients
- Known hypersensitivity to sulphonamides
- Patients who have experienced asthma, acute rhinitis, nasal polyps, angioneurotic oedema, urticaria or other allergic-type reactions after taking acetylsalicylic acid or NSAIDs including COX-2 inhibitors
- Inflammatory bowel disease

- Patients with ongoing requirements for fluconazole or ketoconazole therapy
- Patients with ongoing requirement for lithium therapy
- Patients with ongoing requirement for ACE inhibitor therapy
- Patients who are anticoagulated

## 7. RANDOMISATION

A Randomisation Form (& Eligibility Form) must be completed prior to randomisation. These details should be telephoned or faxed through to the Randomisation Office at the Cancer Research UK Clinical Trials Unit, University of Birmingham.

### RANDOMISATION

(9:00am till 5:00pm, Monday to Friday)

☎ [name] or [name]

✉ [name]

During the randomisation procedure eligibility criteria and randomisation details will be confirmed and verification that the patient has signed the NEO-EXCEL Informed Consent Form will be requested. A unique sequential Trial Number (TNO) will be allocated. This number should be used on all Case Report Forms (CRFs) and all subsequent correspondence relating to that patient. The TNO and allocated treatment must also be recorded on the Randomisation Form, and the Form then signed and dated. The completed original Forms should be sent to the NEO-EXCEL Study Office, with copies retained at site. Confirmation of the randomised treatment allocation will be sent to the Investigator and appointed Pharmacist.

Randomisation will be stratified by tumour size (>2-5cm, >5cm), grade (I, II, III), ER Q-score (3-4, 5-6, 7-8), Her2 (-ve, +ve, not determined), and low dose aspirin use (yes, no). This information therefore must be available at randomisation. A computerised minimisation algorithm, developed by the Trials Unit, will be used to ensure that allocation of treatment to patients is balanced within these strata.

## 8. TREATMENT DETAILS

### 8.1 Trial plan

**Treatment should begin within 5 working days of randomisation. The planned duration of treatment is 16 weeks.**

## **Subjects will be randomised (1:1:1:1) to receive either:**

### **Exemestane + Celecoxib**

Patients will receive exemestane 25mg, one tablet daily and celecoxib 400mg, one capsule twice daily

### **Exemestane + Celecoxib-Placebo**

Patients will receive exemestane 25mg, one tablet daily and celecoxib-placebo, one capsule twice daily

### **Letrozole + Celecoxib**

Patients will receive letrozole 2.5mg, one tablet daily and celecoxib 400mg, one capsule twice daily

### **Letrozole + Celecoxib-Placebo**

Patients will receive letrozole 2.5mg, one tablet daily and celecoxib-placebo, one capsule twice daily

Treatment in all arms will continue until the day of surgery (patients should not take study medication after requirement of 'nil by mouth' for anaesthetic purposes). The surgical date should be planned in advance and will be between 16 weeks and 18 weeks from the commencement of treatment. Sufficient drug supplies will be included to cover this 2-week window.

Dose modifications of trial treatment are not permitted. Patients who are unable to tolerate the trial treatment should be withdrawn from study.

Patients whose tumours progress during the neoadjuvant phase will be withdrawn from study and treated according to local practice.

## **8.2 Concomitant medication**

Patients on oestrogen replacement therapy (HRT) at diagnosis should discontinue this at the time they start trial treatment. Treatment of menopausal symptoms may be initiated as per local protocol during the treatment phase. Systemic oestrogen therapy is prohibited and if required patients must come off study.

### **Aspirin**

NSAIDS and COX 2 inhibitors (except as study medication) are prohibited during the study, except for low dose aspirin. Celecoxib is not a substitute for acetylsalicylic acid for prophylaxis of ischaemic heart disease because of the lack of effect on platelet function. Because celecoxib does not inhibit platelet aggregation antiplatelet therapies should not be discontinued. Therefore continuation of low dose aspirin (75mg daily) is permitted.

### **Fluconazole & Ketoconazole**

Clinical studies have identified potentially significant reactions of celecoxib with fluconazole and ketoconazole. Concomitant administration of fluconazole at 200mg once daily resulted in a 2-fold increase in celecoxib plasma concentration. This increase is due to the inhibition of

celecoxib metabolism via CYPP450 2C9 by fluconazole. Patients on these medications are not eligible.

### **ACE inhibitors**

There is a potential for interactions with ACE inhibitors as inhibition of prostaglandins may diminish their antihypertensive effect. Patients taking ACE inhibitors are excluded from this study.

### **Lithium**

In healthy subjects, lithium concentrations are increased approximately 17% in subjects receiving lithium together with celecoxib. Patients on lithium are not eligible for this study.

### **Diuretics**

Clinical studies have shown that NSAIDS, in some patients, can reduce the natriuretic effect of frusemide and thiazides by inhibition of renal prostaglandin synthesis. Caution is advised for patients on diuretics.

### **Warfarin**

Because of possible interference with INR and also due to multiple biopsies being required, patients on warfarin are ineligible. Tumour measurements may also be affected by excessive bleeding.

Caution is advised when patients are receiving drugs with a narrow therapeutic index and which are mainly dependant on cytochrome CYP 450 enzymes 2A6 and 2C19.

## **8.3 Surgery**

Surgery appropriate to the tumour size determined at the end of treatment will be performed according to national and local guidelines.

### **Complete clinical response**

All patients require surgery. Even if no tumour is palpable or visible on ultrasound to allow an ultrasound marker then a wide local excision of the tumour site should be performed. Some centres with appropriate expertise may choose to insert clips at the same time as the day 14 biopsy in smaller tumours so that if complete clinical response occurs wide local excision can be centred on the clip.

## **8.4 Postoperative management**

Postoperative management will depend on operative pathology and be determined by local protocol. It is expected that all patients will receive a total of 5 years endocrine therapy; continuation of aromatase inhibitor therapy is recommended.

## 9. SCHEDULE OF ASSESSMENTS

The schedule of assessments and investigations required is described below and summarised in Figure 1. This information should be recorded in the patient notes where not explicitly required in the Case Report Forms.

### At Screening

- Relevant medical history including:
  - cardiac history
  - thromboembolic history
  - rheumatological history
  - other serious acute or chronic conditions
- Concomitant medication (description of other medication prescribed for more than 7 days and taken within one month of randomisation)
- ECOG performance status (Appendix 1)
- Clinical examination, including height and body weight
- Uni-dimensional tumour measurement by calipers of the greatest dimension
- Tumour assessment by ultrasound
- Base-line blood tests: full blood count; urea + creatinine + electrolytes; liver function tests
- Blood pressure measurement
- NYHA classification (see section 6.2)

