### Every 4 weeks, on treatment

- Clinical examination
- Treatment side-effects and events
- Uni-dimensional tumour measurement by calipers of the greatest dimension

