## On completion of treatment (no more than 2 weeks prior to surgery)

- Clinical examination
- Treatment side-effects and events
- Uni-dimensional tumour measurement by calipers of the greatest dimension
- Tumour assessment by ultrasound – response will be assessed by RECIST criteria (Appendix 4)
- Routine blood tests including full blood count; urea + creatinine + electrolytes; liver function tests
- Trans NEO-EXCEL bloods
- Additional tumour tissue to be frozen that has been cut from surgical specimen by pathologist (**only for sites participating in the frozen tissue sub-protocol**)
- Formalin-fixed tumour tissue cut from surgical specimen by pathologist

---

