## FIGURE 1: FLOWCHART OF ASSESSMENTS

This table provides a summary of the trial-related procedures required; refer also to full text in section 9

YEAR	1						FOLLOW-UP
	S 	B 	2	3	4	5	
Visit							
Timeframe		Day 1	Day 14	4 wks	8 wks	12 wks	16 wks
Medical history	X						
Clinical examination	X	X		X	X	X	X
Events 				X	X	X	X
Adverse Events/SAEs 			X	X	X	X	X
Tumour assessment by calipers	X			X	X	X	X
Tumour assessment by ultrasound	X						X
Routine bloods	X						X
Trans NEO-EXCEL Bloods		X	X				X
Core Biopsy		X	X				
Formalin fixed tumour tissue cut from surgical specimen							X*

FROZEN TISSUE SUB-PROTOCOL Frozen core biopsies** and frozen sample from* surgical specimen		X**	X**				X*	
--	--	-----	-----	--	--	--	----	--

The Trans NEO-EXCEL sub-protocol is applicable to all sites

The frozen tissue sub-protocol will only apply to sites that are participating in frozen tissue collection

If for any reason Trans NEO-EXCEL blood samples cannot be taken always send all pathology samples

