### Notes:

Medical history to include clinical examination, height, weight, ECOG status, concomitant medication.

1 - Screening visit

2 - Baseline visit (to take place *up to* 5 days before treatment start)

3 - Breast cancer events and survival (disease progression or recurrence, death with cause)

4 - As described in section 13

\*\*Frozen core biopsies \* From surgical specimen

If patients are withdrawn due to disease progression a core biopsy should be performed prior to initiation of alternative treatment and Trans NEO-EXCEL blood samples should also be taken

Patients should continue to take their trial medication until the day of surgery (patients should not take study medication after requirement of 'nil by mouth' for anaesthetic purposes)

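### Blood pressure is required at screening only, and at no visit during 16 to 18 weeks of celecoxib 800 mg/day or placebo

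*Protocol*

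**What the plan says.** Section 9 opens by stating that it describes the required assessments and that Figure 1 summarises them. The screening list contains "Blood pressure measurement" on its own line, apart from the clinical examination with height and weight. The later lists do not repeat it. The four-weekly list has a clinical examination, side-effects and events, and "Uni-dimensional tumour measurement by calipers of the greatest dimension". The completion list adds ultrasound, research samples and "Routine blood tests including full blood count; urea + creatinine + electrolytes; liver function tests".

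Figure 1 introduces itself with "This table provides a summary of the trial-related procedures required; refer also to full text in section 9". It has no blood-pressure row at any visit. Its note on one composite row reads "Medical history to include clinical examination, height, weight, ECOG status, concomitant medication", again without blood pressure.

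Elsewhere the protocol treats blood pressure as relevant to celecoxib:
- Section 6.2 includes among the contraindications "ischaemic heart disease, cerebrovascular disease, uncontrolled hypertension".
- Section 8.2 excludes patients on ACE inhibitors because "inhibition of prostaglandins may diminish their antihypertensive effect".
- Section 8.2 also notes that NSAIDs can weaken the sodium-excreting action of frusemide and thiazides, but there the only instruction is "Caution is advised for patients on diuretics".
- Section 8.1 sets celecoxib at 400 mg twice daily, planned for 16 weeks and continued to surgery at 16 to 18 weeks.

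**The concern.** A contraindication that is checked once at entry can still develop on treatment. The protocol accepts that prostaglandin inhibition can blunt blood-pressure control, and it removes one class of patients for that reason. It keeps diuretic users, whose drugs it says may also be weakened, and attaches no monitoring to the caution. The group is wider than diuretic users. Only uncontrolled hypertension is excluded, and ACE inhibitors are the only antihypertensive class named in the exclusions, so patients whose pressure is controlled on other drugs are eligible.

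Raised blood pressure often causes no symptoms, so asking about side-effects may not reveal it. If no reading is required, a rise reaches neither the treating clinician nor the toxicity data unless a site measures it on its own initiative. What is at stake is the safety of individual patients during treatment, and the completeness of the blood-pressure data available for the celecoxib versus placebo comparison.

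**Working it through.** The protocol states no figure to reproduce. The check is a reading of each visit list, followed by simple counts.

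**Step 1: where a reading is required (section 9 lists).**

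| Visit | Clinical examination | Callipers | Blood pressure |
|---|---|---|---|
| Screening | yes | yes | yes |
| Baseline | yes | no | no |
| Day 14 | no | no | no |
| Week 4 | yes | yes | no |
| Week 8 | yes | yes | no |
| Week 12 | yes | yes | no |
| Week 16 / completion | yes | yes | no |

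Over weeks 4, 8, 12 and 16, examination is required at 4 of 4 visits, callipers at 4 of 4 and blood pressure at 0 of 4. Counting day 14 as well, blood pressure is required at 0 of 5 on-treatment contacts. The long-term follow-up list does not contain it either.

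**Step 2: does the clinical examination already include it?** At screening the authors listed both, as separate items. On that usage, an examination listed alone does not carry a required reading.

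**Step 3: exposure with no required reading (section 8.1).**
- Daily dose in the celecoxib arms: 2 × 400 mg = 800 mg.
- Treated period without a required reading: the whole of it, 16 to 18 weeks.
- Study capsules taken, celecoxib or placebo: 16 × 7 × 2 = 224, up to 18 × 7 × 2 = 252. This restates duration and is not a measure of harm.
- Patients allocated to celecoxib: two of four equal arms of 250, so 2 × 250 = 500 of 1000. This is the exposed group, not the number expected to have a rise.

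**Step 4: after the change.** With readings at weeks 4, 8, 12 and 16, the longest on-treatment interval without one falls from 16–18 weeks to 4 weeks on the Figure 1 timetable. The number of added readings is at most 4 × 1000 = 4,000.

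**What cannot be computed.** The protocol gives no number of diuretic users and no rate or size of blood-pressure rise, so no count of missed rises is offered.

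**The case against.** The strongest reply is that nothing here contradicts itself. The screening reading serves an entry criterion, and asking for more readings is a request for additional monitoring. The diuretic paragraph speaks of sodium excretion, not blood pressure, and no passage says that celecoxib raises pressure in the patients who are admitted. Safeguards exist: the cardiovascular, renal and ACE-inhibitor exclusions; an examination and side-effect review at four visits; an adverse-event definition in section 13.1 broad enough to include any unfavourable sign; creatinine and electrolytes at completion; IDMC review of toxicity; and a short exposure. Figure 1 is only a summary and omits even the screening reading. The case report forms are not shown and might ask for blood pressure.

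Much of this stands, and it limits the weight of the point. Figure 1 is weak support; the evidence is the section 9 lists themselves. The link to diuretic users is an inference from the two paragraphs of section 8.2 read together. The content of the forms is unknown, although a form field would not by itself make the reading part of the required schedule.

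The safeguards do not close the gap. The exclusions act at entry. Adverse-event reporting picks up a symptomless rise only if someone has measured it. The repeat blood tests come when treatment is nearly over. The IDMC first meets on data from 400 patients, about 200 of them on celecoxib under equal allocation, and it cannot review pressures that were not recorded.

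**Conclusion.** The point holds. The protocol names uncontrolled hypertension as a contraindication to celecoxib but requires no blood-pressure reading at any of the four visits at weeks 4, 8, 12 and 16, so the full 16 to 18 weeks of treatment can pass without one. The conclusion rests on reading section 9 as the list of what is required, as it describes itself, and on treating the separate screening entry as showing that an examination does not include a reading.

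The size is modest. Some sites will measure anyway, the number of patients affected is unknown, and no bias between arms is claimed. The primary response comparison, the power and the error rates are untouched. It should be corrected because the omission bears on patient safety and is cheap to repair. An analysis plan could not supply data that were never collected.

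**What to change.** Add a recorded blood-pressure reading to the four-weekly list (weeks 4, 8 and 12) and to the completion list (week 16) in section 9, and add a blood-pressure row to Figure 1 that also shows the screening reading. Provide a field on the on-treatment forms. Include the readings, by celecoxib versus placebo, in the toxicity data given to the IDMC under sections 10.8 and 14.4. Action on an individual reading stays with the treating clinician; since section 8.1 does not allow dose changes, the reading informs the decision whether to continue or withdraw.

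The cost is one cuff reading and one form field at each of four visits that already include a clinical examination, at most 4,000 readings over the trial. No extra visit or invasive procedure is needed.

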### At Baseline

- Clinical examination
- Core biopsy - if insufficient material left from diagnostic core biopsy. (See separate Pathology Consent Form. If this Consent Form is used before diagnostic biopsy and sufficient cores taken, other additional biopsies will not be necessary at baseline).
- Frozen core biopsy (**only for sites participating in the frozen tissue sub-protocol**)
- Trans NEO-EXCEL bloods (pre-treatment)

### At Day 14

- Treatment side-effects
- Core biopsy
- Frozen core biopsy (**only for sites participating in the frozen tissue sub-protocol**)
- Trans NEO-EXCEL bloods

### Every 4 weeks, on treatment

- Clinical examination
- Treatment side-effects and events
- Uni-dimensional tumour measurement by calipers of the greatest dimension

## On completion of treatment (no more than 2 weeks prior to surgery)

- Clinical examination
- Treatment side-effects and events
- Uni-dimensional tumour measurement by calipers of the greatest dimension
- Tumour assessment by ultrasound – response will be assessed by RECIST criteria (Appendix 4)
- Routine blood tests including full blood count; urea + creatinine + electrolytes; liver function tests
- Trans NEO-EXCEL bloods
- Additional tumour tissue to be frozen that has been cut from surgical specimen by pathologist (**only for sites participating in the frozen tissue sub-protocol**)
- Formalin-fixed tumour tissue cut from surgical specimen by pathologist

---

**Please refer to separate Trans NEO-EXCEL lab manuals for full details of sample preparation and collection**

---

### Disease progression

Disease progression is defined by RECIST criteria as an increase in the largest uni-dimensional tumour measurement by > 30%. Response will be assessed by RECIST criteria at every visit. If disease progression does occur, taking into account accepted operator variability, patients will be withdrawn and a biopsy taken as soon as possible and before commencement of alternative therapy. Full details of disease progression/death should be recorded on the trial CRFs.

A summary of treatment offered at progression will also be requested. Sites are strongly urged to take serum/plasma samples, core biopsies (and for sites participating in the frozen tissue sub-protocol, an additional core biopsy to be frozen) as these may help provide invaluable information about the mechanisms of treatment failure.

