### 10.3 Early withdrawal from trial treatment

Patients should be withdrawn from the trial if there is evidence of disease progression. Patients can also be withdrawn at the discretion of the Investigator or at the patient's own request. *Patients have the right to withdraw from the trial at any time for any reason.* Full details of the reason(s) for withdrawal should be recorded on the CRFs if clinician-initiated, otherwise a simple statement reflecting patient preference will suffice.

Please note that patients who withdraw from trial treatment will not be regarded as having withdrawn consent for ongoing follow-up and data collection unless clearly specified at time of withdrawal, and should therefore be followed-up in accordance with the protocol.

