## Progression-free survival

Progressive disease is defined by the tumour growing significantly or new tumours appearing. Progression-free survival is defined as the time from date of trial entry to date when progression is first observed and is censored at date last seen free of local recurrence in those patients who have not experienced the event.

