## **RESPONSE CRITERIA**

### **Evaluation of target lesions**

- \* Complete Response (CR): Disappearance of all target lesions.
- \* Partial Response (PR): At least a 30% decrease in the sum of the LD of target lesions, taking as reference the baseline sum LD.
- \* Progressive Disease (PD): At least a 20% increase in the sum of the LD of target lesions, taking as reference the smallest sum LD recorded since the treatment started or the appearance of one or more new lesions.
- \* Stable Disease (SD): Neither sufficient shrinkage to qualify for PR nor sufficient increase to qualify for PD, taking as reference the smallest sum LD since the treatment started.

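### Section 9 labels growth above 30% as RECIST progression, but the protocol's own RECIST appendix sets 20% over the smallest measurement, or a new lesion

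*Protocol*

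**What the plan says.** The paragraph on progression in Section 9 of the protocol reads: "Disease progression is defined by RECIST criteria as an increase in the largest uni-dimensional tumour measurement by > 30" (per cent). It does not say whether the increase is counted from baseline or from the smallest value, and it does not mention new lesions. The same paragraph asks for RECIST response assessment at each visit and continues: "If disease progression does occur, taking into account accepted operator variability, patients will be withdrawn and a biopsy taken as soon as possible".

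Appendix 4 reproduces RECIST, and Section 9 cites it by number for the end-of-treatment ultrasound. Its rule is "Progressive Disease (PD): At least a 20% increase in the sum of the LD of target lesions, taking as reference the smallest sum LD" since treatment started, or one or more new lesions. The 30% figure among its target-lesion criteria belongs to response: "Partial Response (PR): At least a 30% decrease in the sum of the LD of target lesions, taking as reference the baseline sum LD".

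Two other sections act on progression without defining it. Section 8.1: "Patients whose tumours progress during the neoadjuvant phase will be withdrawn from study and treated according to local practice". Section 10.3: "Patients should be withdrawn from the trial if there is evidence of disease progression".

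Section 14.1, under progression-free survival, gives a description with no number: "Progressive disease is defined by the tumour growing significantly or new tumours appearing".

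**The concern.** Section 9 claims RECIST as its source and then departs from the protocol's own copy of RECIST in three respects: the size of the increase, the measurement it is counted from, and new lesions. The 30% looks like the partial-response figure carried over to progression, although the document does not say how it arose.

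Progression is a trigger for action. Callipers are applied every 4 weeks, and a patient judged to have progressed leaves trial treatment, has a biopsy and moves to local therapy. Two sites that each follow the protocol could handle the same measurement in opposite ways. An analysis plan could recode a progression date later, but it could not undo a withdrawal.

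Progression-free survival, a secondary outcome, runs from trial entry, so progression before surgery counts as an event. A single objective rule is also worth having because only celecoxib has a placebo (Section 8.1). The exemestane–letrozole comparison therefore appears to be the open-label one mentioned in Section 5.

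**Working it through.** **Inputs**

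- Section 9: increase above 30% in the largest single dimension; reference not stated.
- Appendix 4: increase of at least 20% over the smallest sum since treatment started, or a new lesion.
- Appendix 4: partial response is a decrease of at least 30% from baseline.
- Example sizes: 20 mm is the lower size limit for entry (Section 6.1, above 2 cm on ultrasound) and 50 mm is the stratification cut (Section 7). The 40 mm and 30 mm values are assumed for illustration. The 28 mm value is the partial-response limit for a 40 mm tumour: 0.7 × 40 = 28.

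With one measured breast tumour, the sum of longest diameters is that tumour's diameter, so the two rules can be compared directly.

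**Can Section 9's figure be obtained from the source it names?** No. Appendix 4 gives 20% for growth; its 30% is for shrinkage.

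**Formulas.** Let *b* be the baseline and *m* the smallest measurement so far, baseline included.

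- Appendix 4: progression at 1.2 × *m* or more.
- Section 9 counted from the smallest value: above 1.3 × *m*.
- Section 9 counted from baseline: above 1.3 × *b*.

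| *b* (mm) | *m* (mm) | Appendix 4, at or above | Section 9 from smallest, above | Section 9 from baseline, above | Gap (mm) |
|---|---|---|---|---|---|
| 20 | 20 | 24 | 26 | 26 | 2 |
| 40 | 40 | 48 | 52 | 52 | 4 |
| 50 | 50 | 60 | 65 | 65 | 5 |
| 40 | 30 | 36 | 39 | 52 | 3 or 16 |
| 40 | 28 | 33.6 | 36.4 | 52 | 2.8 or 18.4 |

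If both rules use the smallest value, the gap is 1.3*m* − 1.2*m* = 0.1*m*, that is 10% of the reference measurement. If Section 9 is counted from baseline, the gap is 1.3*b* − 1.2*m*, which widens as the tumour responds. For *b* = 40 and *m* = 28 it is 52 − 33.6 = 18.4 mm.

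Take that last tumour regrown from 28 mm to 40 mm. Growth from the smallest value is 40/28 − 1 = 43%, which is progression under Appendix 4 and under Section 9 counted from the smallest value. Counted from baseline, growth is 40/40 − 1 = 0%, so there is no progression.

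**New lesions.** A new lesion with no growth of the measured tumour is progression under Appendix 4 and under Section 14.1. Section 9's definition does not cover it.

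**What does not change.** The primary outcome in Section 14.1 is a calliper decrease of at least 30% or no palpable lesion, and it does not use progression. The sample size in Section 14.3 does not use the threshold either.

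**The case against.** The conflict in the numbers is not in dispute, but several points narrow it.

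- *The protocol as a whole is not silent.* Because Section 9 invokes RECIST, a reader can take the reference value and the new-lesion rule from Appendix 4, and Section 14.1 also counts new tumours. This is true, but Section 9 states its own definition, and a site working from that sentence has neither element. The omission is specific to Section 9.
- *Section 9 is the trial-specific text and so should prevail.* Appendix 4 is a generic quick reference, and Section 9 cites it by number only for ultrasound. A site could reasonably use Section 9 as its working rule. However, no text gives it precedence, and it would still lack a reference measurement and still be wrongly labelled RECIST.
- *Thirty per cent may be a deliberate allowance for calliper error.* The document does not say so. Operator variability appears as a separate qualification with no number.
- *Investigators have discretion.* Section 10.3 lets them withdraw a patient in any case, so neither threshold is purely mechanical. This stands, and it softens the claim that a patient between the limits would necessarily continue.
- *The large gaps depend on the reading.* The 16 mm and 18.4 mm figures require counting from baseline after shrinkage. Counted from the smallest value, the more natural RECIST reading, every gap in the table is 2 to 5 mm. This stands too; the wide gaps show the cost of leaving the reference unstated.
- *The effect on outcomes is small.* The primary outcome is untouched, and patients who stop treatment stay in follow-up unless they withdraw consent for it. This is accepted, and it limits the severity.

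**Conclusion.** The concern holds. Section 9 attributes to RECIST a threshold that the protocol's own RECIST text contradicts, and it leaves out the reference measurement and new lesions. Neither the operator-variability clause nor Section 14.1's unquantified wording resolves the difference.

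The disagreement is 10% of the smallest measurement if both rules use that reference, or 2 to 5 mm in the examples. It reaches 16 to 18.4 mm in the two shrinking examples if Section 9 is counted from baseline. These figures assume a single measured lesion and illustrative tumour sizes. The number of patients affected cannot be estimated from the documents.

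The consequences are confined to withdrawal and biopsy during neoadjuvant treatment and to progression-free survival before surgery. The point should be fixed, but it does not threaten the primary analysis.

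**What to change.** In Section 9, replace the 30% rule with that of Appendix 4: an increase of at least 20% over the smallest calliper measurement since treatment started, baseline included, or any new lesion. The operator-variability allowance can stay as clinical judgement. It would remain unquantified, so a stated margin would be better if the team has one to hand.

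If 30% is intended, state the reference measurement, add new lesions, remove the attribution to RECIST, and note the departure in Appendix 4.

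In either case, have Section 14.1 refer to the chosen rule for progression-free survival events before surgery. Its wording on later relapse can stay.

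The cost is a change of protocol wording, the approval that an amendment needs (Section 15.1), and a memo to sites. No new visits or data are required.
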